7.2.1 Sample Size Justification

As the most clinically important aims, aims 1-2 will be used as the basis for the sample size analysis, where each patient represents an independent data point used to evaluate the technique's sensitivity and specificity at both 1-2 weeks and 1 month follow-up times. Based on our pilot studies using 2D CEUS to evaluate TACE performed using Lipiodol [Kono et al. 2007] or drug-eluting-beads [Shaw et al. 2014], we expect to encounter a patient population in which up to 67% of patients require retreatment. A sample size analysis was performed using a binomial test with One-Sample Sensitivity and Specificity Analysis in NCSS/PASS 2008 (NCSS, East Kaysville, UT) to estimate the number of cases required to produce a over 85% power for this study. This analysis assumes sensitivity and specificities of 98%, an alpha of 0.05, prevalence of disease of 66.7%, and null sensitivity and specificities of 90%. Results from this analysis are provided in tabular format below.

Preva- ---- Power ----		Sample	--- Sensitivity ---		--- Specificity ---		----- Alpha -----			P
Size	H0 Sens. Spec.	H1 N1 and N	H0 Se0	H1 Se1	Sp0	Sens. Sp1	Spec. Target	lence Actual	Actual	P
0.0000	0.0000	7								
10	0.9000	0.9800	0.9000	0.9800	0.0500	0.0000	0.0000	0.6670		
0.0000	0.0000	13								
20	0.9000	0.9800	0.9000	0.9800	0.0500	0.0000	0.0000	0.6670		
0.0000	0.0000	20								
30	0.9000	0.9800	0.9000	0.9800	0.0500	0.0000	0.0000	0.6670		
0.0000	0.0000	27								
40	0.9000	0.9800	0.9000	0.9800	0.0500	0.0000	0.0000	0.6670		
0.5134	0.0000	33								
50	0.9000	0.9800	0.9000	0.9800	0.0500	0.0309	0.0000	0.6670		
0.4457	0.0000	40								
60	0.9000	0.9800	0.9000	0.9800	0.0500	0.0148	0.0000	0.6670		
0.7581	0.0000	47								
70	0.9000	0.9800	0.9000	0.9800	0.0500	0.0440	0.0000	0.6670		
0.7135	0.0000	53								
80	0.9000	0.9800	0.9000	0.9800	0.0500	0.0259	0.0000	0.6670		
0.6619	0.5455	60								
90	0.9000	0.9800	0.9000	0.9800	0.0500	0.0138	0.0424	0.6670		
0.8494	0.5134	67								
100	0.9000	0.9800	0.9000	0.9800	0.0500	0.0307	0.0309	0.6670		
0.8202	0.4735	73								
110	0.9000	0.9800	0.9000	0.9800	0.0500	0.0190	0.0203	0.6670		
0.9231	0.4457	80								
120	0.9000	0.9800	0.9000	0.9800	0.0500	0.0353	0.0148	0.6670		
0.9027	0.4195	87								
130	0.9000	0.9800	0.9000	0.9800	0.0500	0.0211	0.0108	0.6670		
0.9608	0.7581	93								
140	0.9000	0.9800	0.9000	0.9800	0.0500	0.0382	0.0440	0.6670		

0.9492	0.7358	100							
150	0.9000	0.9800	0.9000	0.9800	0.0500	0.0237	0.0338	0.6670	
0.9791	0.7135	107							
160	0.9000	0.9800	0.9000	0.9800	0.0500	0.0374	0.0259	0.6670	
0.9735	0.6839	113							
170	0.9000	0.9800	0.9000	0.9800	0.0500	0.0255	0.0181	0.6670	
0.9893	0.6619	120							
180	0.9000	0.9800	0.9000	0.9800	0.0500	0.0382	0.0138	0.6670	
0.9857	0.8879	127							
190	0.9000	0.9800	0.9000	0.9800	0.0500	0.0250	0.0421	0.6670	
0.9945	0.8494	133							
200	0.9000	0.9800	0.9000	0.9800	0.0500	0.0385	0.0307	0.6670	

A total of 201 patients will be used in the final analysis for this study (the first 9 will be used as training cases and excluded), of which 135 (66.7%) will require retreatment. A total sample size of 201 (which includes 133 subjects with the disease) achieves 99% power to reject the null hypothesis for sensitivity, and 85% power to reject the null hypothesis for specificity.

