7.2 Statistical Analyses

Data analysis from this multi-center clinical trial will be performed to characterize 2D and 4D CEUS as a follow-up imaging tool for the evaluation of residual tumoral blood flow in patients with HCC treated with TACE.

Our statistical analysis will address three major questions:

1. Does 2D and 4D CEUS 1-2 weeks post TACE yield sensitivity and specificity greater than 90% for identifying residual tumor blood flow, thereby providing reliable earlier identification (relative to the current clinical standard) of patients in need of retreatment?
2. Does 2D and 4D CEUS 1 month post TACE yield sensitivity and specificity greater than 90% for identifying residual tumor blood flow, thereby providing an accurate, safe, and cost-effective imaging alternative for identifying TACE patients in need of retreatment?
3. Are quantifiable biomarkers generated by parametric imaging of 2D and 4D CEUS exams able to differentiate between fully treated and incompletely treated masses by measuring blood flow kinetics?

The first three cases at each institution will be used as reader training cases and will not be included in the final analysis. In the event of all cases showing identical response (i.e. all incompletely or completely treated), the first case with an alternative outcome will be substituted for the 9th case. Following reader training, each reader (all of whom have previous experience with CEUS and volumetric ultrasound) will be asked to evaluate all 201 remaining cases. 2D and 4D CEUS exams will be read separately and only after randomization. 2D cases will be viewed in a standard DICOM viewer, while 4D cases will be viewed in GE's 4D View software. Readers will first be asked to review both the patient's baseline CE-MRI/CT and CEUS exams to identify the size and location of the treated mass. Following baseline review, each reader will review the 1-2 week and 1 month CEUS exam (in random order). Intratumoral blood flow will be assessed as present or not present. Readers will then be asked to interpret the patient's 1 month follow-up CE-MRI/CT images and again evaluate the need to retreat based on residual blood flow. Finally, when available, readers will review subsequent CE-MRI/CT imaging studies (up to six months post TACE). MRI/CT evaluations will be based on mRECIST criteria. All imaging studies will be read twice by each

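### Section 7.2.1 presents single-test powers as power for the study; passing sensitivity and specificity together has 84.0 to 84.9% power per mode and time point, and less if 2D and 4D must both pass

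*Combined protocol and SAP*

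**What the plan says.** Section 7.2 frames the main analysis as questions. Question 1 reads "Does 2D and 4D CEUS 1-2 weeks post TACE yield sensitivity and specificity greater than 90% for identifying residual tumor blood flow", and question 2 asks the same at 1 month. Section 7.2 then sets up a separate 2 x 2 table for each of the four CEUS groups (2D and 4D, each at 1-2 weeks and 1 month). It requires significance at 0.05 after a Bonferroni-type adjustment and does not give the number of tests.

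Section 7.2.1 bases the sample size on the aims behind these questions. The calculation was done "using a binomial test with One-Sample Sensitivity and Specificity Analysis in NCSS/PASS 2008", with true values of 98%, null values of 90%, alpha 0.05 and prevalence 66.7%. Its aim was "to estimate the number of cases required to produce a over 85% power for this study". The conclusion is that the sample "achieves 99% power to reject the null hypothesis for sensitivity, and 85% power to reject the null hypothesis for specificity".

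The closing paragraph gives two counts of patients needing retreatment among the 201 analysed: "of which 135 (66.7%) will require retreatment" and "A total sample size of 201 (which includes 133 subjects with the disease". The section gives no joint power, does not mention that two modes are evaluated, and makes no assumption about the correlation between 2D and 4D.

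**The concern.** The questions are worded as conjunctions, while the power figures each refer to one test in one CEUS group. A mode that passes on sensitivity and fails on specificity has not shown both to exceed 90%. The relevant power is therefore the probability that both tests reject, which is lower than either power alone.

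Two things are at stake. The stated power describes something other than the question asked. And without a written success rule, a mixed result (sensitivity passes and specificity fails, or 4D passes and 2D fails) could be read as success or failure after the data are seen.

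**Working it through.** **Inputs, all from section 7.2.1.** Null 0.90, alternative 0.98, alpha 0.05 per test. The table row for N = 200 has 133 patients needing retreatment, which leaves 200 - 133 = 67 who do not. Its powers are 0.9945 and 0.8494. The section does not state sidedness, but the table's actual alphas match a one-sided test only.

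**Step 1: reproduce the plan's figures.** The exact one-sided binomial test takes the smallest r with P(X >= r | n, 0.90) <= 0.05; power is P(X >= r | n, 0.98).

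- Sensitivity: n = 133, r = 126, actual alpha 0.0385, power 0.9945.
- Specificity: n = 67, r = 65, actual alpha 0.0307, power 0.8494.

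Both agree with the table to four decimals. A two-sided version (0.025 per tail) would give 0.9820 and 0.6115, which does not match.

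**Step 2: one mode at one time point, both tests pass.** Sensitivity uses patients who need retreatment and specificity uses those who do not. The groups are disjoint, so the powers multiply: 0.9945 x 0.8494 = 0.845.

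The paragraph's counts allow other splits of 201: 201 - 133 = 68, 201 - 135 = 66, and 0.667 x 201 = 134, which leaves 67.

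| Split (retreat / not) | Sensitivity power | Specificity power | Both pass |
|---|---|---|---|
| 133 / 67 | 0.9945 | 0.8494 | 0.845 |
| 133 / 68 | 0.9945 | 0.8446 | 0.840 |
| 134 / 67 | 0.9942 | 0.8494 | 0.845 |
| 135 / 66 | 0.9940 | 0.8541 | 0.849 |

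The range is 84.0 to 84.9%, short of 85% by 0.1 to 1.0 points.

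**Step 3: both modes required at one time point.** 2D and 4D are read in the same patients, so the result depends on the correlation phi between their errors. The documents do not give phi; it is an assumption here. With error rate 0.02 in each mode, the probability that both are wrong is 0.02 x 0.02 + phi x 0.02 x 0.98, and the probability that only a given one is wrong is 0.02 minus that. Summing the multinomial exactly over the outcomes in which both modes pass, then multiplying across the two patient groups, gives at 133/67:

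| phi | 0 | 0.25 | 0.5 | 0.75 | 0.9 | 1 |
|---|---|---|---|---|---|---|
| Power | 0.714 | 0.733 | 0.756 | 0.788 | 0.817 | 0.845 |

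Over the other splits, the value at phi = 0 runs from about 0.706 (133/68) to 0.721 (135/66), and at phi = 1 from 0.840 to 0.849.

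**Step 4: effect of the planned adjustment.** The number of tests is not given, so two examples are shown for one mode at 133/67.

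- Alpha over two questions: 0.05 / 2 = 0.025. Power is 0.9820 x 0.6115 = 0.600.
- Alpha over four mode and time-point groups: 0.05 / 4 = 0.0125. Power is 0.9483 x 0.6115 = 0.580.

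Specificity drives the loss. With 67 patients the critical value moves from 65 to 66 at either level.

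**The case against.** The strongest reply is that the plan never says both modes must succeed. The wording of the questions can be read as listing two techniques. Section 7.2 tabulates the four CEUS groups separately and compares 2D with 4D by ROC area, which suggests that each is judged on its own. On that reading the shortfall is at most about one point. The sentence reporting the result also labels the two powers openly, and the table is correct.

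Much of this stands. There is no arithmetic error in the table, and on the separate reading the gap alone would be minor. What remains is that even one mode needs sensitivity and specificity together, that no split in the paragraph brings this above 85%, and that the text leaves open which rule applies.

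A reader might go further and infer that the trial's true power is 71%, or that all four CEUS groups must pass, which under independence would give about 51% (0.8447 to the fourth power is 0.509). The documents support neither as fact. The first needs a both-modes rule that the wording only suggests, plus independent errors. The second needs a single success criterion across two questions that the plan asks separately.

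**Conclusion.** The stated target is not met for the conjunctive questions in section 7.2, but the certain part of the shortfall is small: 84.0 to 84.9% per mode and time point against a target above 85%. It becomes material only if 2D and 4D must both pass: at 133/67, about 71% with independent errors and about 73% and 76% at phi 0.25 and 0.5. It returns to the per-mode figure only with complete agreement.

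These figures rest on true sensitivity and specificity of 98% in both modes, one-sided alpha 0.05 per test with no multiplicity adjustment, no losses, and the patient counts in section 7.2.1. The pilot studies cited there used 2D CEUS, so 98% for 4D is a further assumption. Once the adjustment required in section 7.2 is applied, per-mode power is nearer 58 to 60% in the two examples above. The underlying defect is an unstated success rule, which is a matter of specification.

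**What to change.** In section 7.2, state that a mode at a time point succeeds only if sensitivity and specificity each reject 90% by the one-sided exact binomial test used for sizing. Because both must reject (an intersection-union rule), alpha need not be split between those two tests. Naming the test matters: the only test section 7.2 now assigns to each CEUS group against the reference standard is McNemar's, which does not test against 90%. State also whether 2D and 4D are judged separately or must both succeed.

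In section 7.2.1, replace the study-level power claim with the joint power under that rule, labelled as unadjusted one-sided alpha 0.05: about 84% per mode and time point, or about 71 to 84% if both modes are required, with the correlation assumption stated. Beside it, give the power at the alpha left after the Bonferroni-type adjustment, once the number of tests is fixed; at 133/67 this is about 60% per mode at 0.025 and 58% at 0.0125. Use one count of patients needing retreatment throughout.

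The cost is a few sentences and a less favourable stated power. Making this correction needs no more patients and changes no trial procedure.

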examination will be obtained from the patient's referring physician. If the subject is a woman of childbearing potential, she will have a urine pregnancy test prior to each CEUS study (the results of which will be made available to the subject prior to study initiation). In the event a patient presents with a lesion that is expected to be difficult to view on ultrasound (for example, smaller lesions located high on the liver dome), grayscale ultrasound imaging will quickly be performed to ensure the lesion is visible on ultrasound and that the patient is suitable for study inclusion.

Patients will undergo a total of three separate CEUS exams. These exams will consist of the baseline study prior to TACE therapy, a study 1-2 weeks post treatment that will coincide with clinical post-procedure follow-up by the interventional radiologist, and a study approximately one month post treatment when patients return for clinically scheduled CE-CT/MRI follow-up. If the patient fails to show up for the 1-2 week CEUS exam, they will not be excluded from the final ultrasound exam. Procedures and equipment for this trial will be used in accordance with standard clinical protocols and good clinical practices already in place at our hospitals.

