During cTACE, iodinated, ester derived poppy-seed oils serve as drug carriers, as temporary embolization material, and as imaging agents under fluoroscopy [Gonsalves and Brown, 2009]. The chemotherapeutic agents used may vary, but most frequently consist of a cisplatin, adriamycin, and mitomycin (CAM) mixture [Van Ha 2009]. Following delivery, more permanent embolization is achieved with materials such as poly-vinyl alcohol or gelfoam [Gonsalves and Brown, 2009]. While cTACE is an effective therapy for slowing disease progression, improved patient responses with less toxicity have been observed with the use of DEB-TACE [Vogl et al. 2011; Lammer et al. 2010; Gaba 2012]. Embolization with DEB-TACE results in occlusion of the tumor vasculature, combined with a sustained, intratumoral release of the chemotherapeutic [Lewis et al. 2006]. Compared with cTACE, DEB-TACE is associated with greater treatment tolerance and significantly less liver toxicity and doxorubicin-related side effects [Vogl et al. 2011, Lammer et al 2010].

Both TACE procedures are performed under fluoroscopic guidance for catheter placement and infusion monitoring, with infusions continuing until near stasis in the tumor-feeding artery is observed [Van Ha 2009]. Access to the tumor vasculature is achieved via a catheter placed in the hepatic artery. Technical

success, defined as correct catheter placement and drug administration, is achieved in approximately 98% of patients [Brown et al. 2012]. Residual tumoral viability at imaging post-embolization is the primary criterion used in determining the need to re-treat. TACE is frequently iterative – up to 65-75% of tumors will demonstrate residual blood flow and require repeat TACE or alternative treatments. The lack of efficacy on the initial treatment may be due to reaching premature stasis because of slow flow conditions, vasospasm limiting delivery, or redistribution of flow to the lesion from an alternative hepatic branch after primary branch occlusion.

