4. TRIAL POPULATION

Trial Population: This trial will consist of up to 210 adults (with a maximum of up to 100 at any institution) undergoing transarterial chemoembolization for the treatment of HCC split between Thomas Jefferson University, The University of California, San Diego, and The Hospital of the University of Pennsylvania. The patients enrolled in this project will be adults over the age of 21 capable of providing informed consent.

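### Section 7.2.1 powers specificity on the enrolment ceiling with no loss allowance and a fixed number of reference-negative patients; averaged over a random number, power is about 83% with no loss and about 77% with an assumed 10% loss, not 85%.

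*Combined protocol and SAP*

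**What the plan says.** Section 4 caps enrolment: "This trial will consist of up to 210 adults". Section 7.2.1 removes the training cases ("the first 9 will be used as training cases and excluded") and takes the whole remainder as the analysis set: "A total of 201 patients will be used in the final analysis for this study". The same number serves the 1-2 week and the 1-month evaluations.

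The design inputs are given in one sentence: "This analysis assumes sensitivity and specificities of 98%, an alpha of 0.05", then "prevalence of disease of 66.7%, and null sensitivity and specificities of 90"%. The method is a one-sample binomial analysis for sensitivity and specificity, the target is more than 85% power, and the result reported is 99% for sensitivity and 85% for specificity.

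Other sections bear on how many patients will be evaluable:

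- Synopsis, Trial Procedures: "If the patient fails to show up for the 1-2 week CEUS exam, they will not be excluded from the final ultrasound exam". Section 3.1 repeats the rule.
- Section 6.7.1 defines discontinued subjects. It gives no expected rate and no replacement rule.
- Section 7.2: "Finally, when available, readers will review subsequent CE-MRI/CT imaging studies (up to six months post TACE"). Two of the four reference criteria in that section rest on 6-month imaging.
- Section 6.2 keeps only one group outside the 210: patients whose mass is not visible on B-mode.

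On prevalence, section 7.2.1 expects at most 67% of patients to need retreatment, the Introduction gives at most two-thirds of patients, and section 1.1 has a per-tumor figure: "up to 65-75% of tumors will demonstrate residual blood flow and require repeat TACE or alternative treatments".

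**The concern.** Specificity is tested in the smaller group, about a third of the patients, so it is the weaker half of a claim that needs both measures above 90%. Its 85% power depends on how many reference-negative patients are actually evaluable. The plan obtains that number from the enrolment maximum, as if nobody were lost, and from a fixed prevalence, as if the split were known in advance.

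An exact binomial test with so few permitted errors does not lose power smoothly. When the number of negatives falls far enough for one fewer false positive to be allowed, power drops abruptly. Whoever relies on the 85% needs to know how close that drop lies. The 1-2 week question carries the case for earlier retreatment and is the one the missed-exam rule exposes.

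**Working it through.** **Inputs.** Null specificity 90%, alternative 98%, alpha 0.05, prevalence 66.7%, analysed N 201 (all section 7.2.1); ceiling 210 (section 4). Sidedness is not stated. Loss rates are my assumptions, because the documents give none.

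**Step 1: reproduce the plan's figure.** For n negatives, find the smallest r with P(X ≥ r | n, 0.90) ≤ 0.05; power is P(X ≥ r | n, 0.98).

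- N=200 row: 200 - 133 = 67 negatives, r = 65 (two false positives allowed), actual alpha 0.0307, power 0.8494. This matches the table and is just under the target of more than 85%.
- Sensitivity: n = 133, r = 126, actual alpha 0.0385, power 0.9945. This also matches.
- With 0.025 per tail, power at 67 negatives would be 61.2%, which does not match. The table is therefore one-sided 0.05.

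**Step 2: the counts in the prose.** With 201 patients, 133 diseased leaves 68 negatives (84.5% power); 135 diseased leaves 66 (85.4%). Both diseased counts appear in the closing paragraph of section 7.2.1. The difference in power is small, but the counts conflict.

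**Step 3: power by number of negatives (one-sided 0.05).**

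| Negatives | False positives allowed | Power |
|---|---|---|
| 60 | 1 | 66.2% |
| 61 | 2 | 87.7% |
| 64 | 2 | 86.3% |
| 67 | 2 | 84.9% |
| 70 | 2 | 83.5% |
| 75 | 2 | 81.0% |

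The plan's own table shows the drop: the N=180 row has 180 - 120 = 60 negatives and prints 0.6619.

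**Step 4: let the number of negatives vary.** Take K ~ Binomial(N, 1 - prevalence) and average: Σ P(K = k) × power(k). With N = 201 and prevalence 0.667 the expected number is 201 × 0.333 = 66.9, and P(K ≤ 60) = 0.168.

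| Evaluable N | Prevalence | Averaged specificity power |
|---|---|---|
| 201 (no loss) | 66.7% | 82.7% |
| 191 (assumed 5% loss) | 66.7% | 80.2% |
| 181 (assumed 10% loss) | 66.7% | 77.1% |
| 201 | 65% | 84.8% |
| 201 | 70% | 77.1% |
| 201 | 75% (per-tumor upper bound) | 66.4% |

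(201 × 0.95 = 190.95 and 201 × 0.90 = 180.9, rounded.)

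**Step 5: sensitivity.** At the expected number of diseased patients, sensitivity power stays above 97% for every combination of 65-75% prevalence and 0-20% loss examined. Sensitivity is not at issue.

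**The case against.** The strongest reply is that nothing here is miscalculated. The 85% follows from the stated inputs, and reporting power at the expected count is what the table sets out to do. That stands: the point concerns assumptions, not arithmetic, apart from the conflict between 133 and 135. With full follow-up, averaging costs about two percentage points (84.9% to 82.7%).

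Four stronger readings are tempting and are not supported.

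- A reader might infer that the design needs exactly 67 negatives. It does not: every number from 61 to 67 gives 84.9-87.7%, and an assumed 5% loss at the expected count (64 negatives) gives 86.3%. The drop is at 60.
- A reader might take 75% as a plausible patient-level prevalence. Section 1.1 gives it per tumor and as an upper limit, whereas section 7.2.1 makes the patient the data point and treats about 67% as an upper limit. A lower prevalence gives more negatives and helps specificity. The 66.4% figure is a stress test only.
- A reader might infer that every patient needs all exams at both times. Section 7.2 builds four separate 2 × 2 tables, so a missed 1-2 week exam removes a patient only from the two 1-2 week tables.
- A reader might conclude that the design will certainly miss its power by a wide margin. The larger shortfalls need loss rates that the documents do not state, or the per-tumor bound.

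The reference standard is also a hierarchy. Explant pathology or angiographic confirmation can classify a patient without 6-month imaging, so uniform loss is only a rough stand-in for missing reference outcomes.

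Finally, all the figures above are for a one-sided unadjusted binomial test. Section 7.2 plans a Bonferroni-type adjustment and names a McNemar test, so any replacement figure must carry that label.

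**Conclusion.** The concern holds in this form. Section 7.2.1 treats a maximum as the analysed number, makes no allowance for losses that the plan itself foresees, and fixes a number of negatives that will vary. Under the plan's own inputs and with no loss at all, averaged specificity power is 82.7%, against a stated 85% and a target of more than 85%. There is roughly a one in six chance (16.8%) of landing at or below 60 negatives; at exactly 60, power is 66.2%. With assumed losses of 5% and 10% the averages are 80.2% and 77.1%.

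The no-loss result rests only on the plan's inputs, one-sided 0.05 and binomial variation in the number of negatives. The loss results add assumed rates, applied evenly to diseased and non-diseased patients. The issue is moderate: a power figure that readers will rely on is somewhat too favourable for specificity, most clearly for the 1-2 week question if exams are missed.

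**What to change.** Revise section 7.2.1 as follows.

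1. Describe 201 as the maximum analysable number, not the number that will be analysed.
2. Reconcile 133 and 135 diseased patients (68 or 66 negatives), and say that the 85% came from the N=200 row with 67.
3. Replace the 85% with specificity power averaged over the random number of negatives: about 83% with no loss and about 77% with an assumed 10% loss. Label both as one-sided 0.05 before any Bonferroni-type adjustment, and label the loss rate as an assumption.
4. State the power separately for the 1-2 week and 1-month analyses, because a missed 1-2 week exam reduces only the former.
5. Show sensitivity to patient-level prevalence on both sides of 66.7%, for example 84.8% at 65% and 77.1% at 70% with no loss. If 75% is shown (66.4%), mark it as an assumption drawn from a per-tumor upper bound.

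No extra patients and no change to procedures are needed. The cost is some redrafting and a less favourable stated power for specificity.

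### Section 7.2.1 gives the retreatment count among 201 patients as both 135 and 133 and attaches the N=200 power to N=201, so whether specificity power exceeds 85% depends on which count is meant

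*Combined protocol and SAP*

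**What the plan says.** Section 7.2.1 (Sample Size Justification) describes the calculation as made "using a binomial test with One-Sample Sensitivity and Specificity Analysis", with the purpose of finding the number of cases needed "to produce a over 85% power for this study". The inputs are given in one sentence: "This analysis assumes sensitivity and specificities of 98%, an alpha of 0.05", "prevalence of disease of 66.7" percent, and "null sensitivity and specificities of 90" percent.

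A power table follows in steps of 10 patients, ending at N=200. That last row shows 133 diseased, power 0.9945 for sensitivity and 0.8494 for specificity, and actual alphas of 0.0385 and 0.0307.

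Two sentences after the table state the result. The first says 201 patients enter the final analysis once nine training cases are set aside, "of which 135 (66.7%) will require retreatment". The second says "A total sample size of 201 (which includes 133 subjects with the disease) achieves 99% power" for sensitivity, and 85% for specificity.

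**The concern.** The two closing sentences describe the same group of patients with different counts, 135 and 133, and the percentage printed beside the 135 fits neither. The power figures are quoted for N=201, although the table was run only to N=200.

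The reference-negative count drives the specificity power, and specificity is the limiting side of this design. With 135 positives there are 201 - 135 = 66 negatives; with 133 there are 68. A reader cannot tell how many negatives the specificity claim assumes. Because the quoted power sits almost exactly on the 85% line, a difference of one or two patients decides whether the plan meets its own stated aim.

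**Working it through.** **Inputs (all from Section 7.2.1).** Null sensitivity and specificity 0.90; alternative 0.98; alpha 0.05; prevalence 66.7%; analysed N = 201; aim, power above 85%. The text does not say whether alpha is one- or two-sided.

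**Method.** For a group of size n, take the smallest r with P(X ≥ r | n, 0.90) ≤ 0.05. Power is then P(X ≥ r | n, 0.98).

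**Step 1: reproduce the plan's N=200 row.** 200 × 0.667 = 133.4, so 133 positive and 67 negative.

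- n = 133: r = 126, actual alpha 0.0385, power 0.9945.
- n = 67: r = 65, actual alpha 0.0307, power 0.8494.

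The second power is the chance of at most two false positives among 67:

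0.98^67 + 67 × 0.02 × 0.98^66 + 2211 × 0.02² × 0.98^65 = 0.2583 + 0.3532 + 0.2379 = 0.8494.

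All four figures match the printed row to four decimals, which identifies the test as one-sided at 0.05. A two-sided equal-tail version gives 0.9820 and 0.6115 and does not match.

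**Step 2: check the counts.**

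- 201 × 0.667 = 134.07, and 134/201 = 66.7%.
- 135/201 = 67.2%.
- 133/201 = 66.2%.

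The 133 is the N=200 count. Carried over to N=201, it implies 68 negatives, not the 67 that produced 0.8494.

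**Step 3: power at N=201 for each possible split.**

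| Positive / negative | r (positive) | Sensitivity power | r (negative) | Specificity power | Against 85% |
|---|---|---|---|---|---|
| 135 / 66 | 128 | 0.9940 | 64 | 0.8541 | above by 0.41 points |
| 134 / 67 | 127 | 0.9942 | 65 | 0.8494 | below by 0.06 points |
| 133 / 68 | 126 | 0.9945 | 66 | 0.8446 | below by 0.54 points |

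**Step 4: would a few more patients help?** Not by themselves. Each specificity rule in the table above allows two false positives. While that allowance is fixed, each added negative lowers the power. Keeping the prevalence at 66.7%, N = 210 has 70 negatives and specificity power 0.835.

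**The case against.** The strongest reply is that nothing of substance turns on this. The figure 0.8494 rounds correctly to 85%, the shortfall under the consistent split is 0.06 points, and sensitivity power is 99% under every count. The prevalence is itself uncertain by far more than one or two patients. Section 1.1 says that up to 65-75% of tumors show residual flow. At 75%, about 50 of 201 would be negative (201 × 0.25 = 50.25), and the plan's own N=150 row, which has 150 - 100 = 50 negatives, puts specificity power at 0.7358. All of this stands, and it is why the point is minor. It does not reconcile 135 with 133, or N=200 with N=201.

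A second reply is that 135 may come from the rounded figure of up to 67% given earlier in the same section: 201 × 0.67 = 134.67, which rounds up to 135. On that reading the error is in the 66.7% label and the count was intended. That is plausible, but the document does not say so. The next sentence still uses 133, and the power calculation used 0.667.

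Two stronger readings should be resisted. One is that the plan simply misses its power target. The documents do not support that without qualification, because under the plan's own 135 count the specificity power is 85.4%. The other is that the power table contains a computing error. The N=190 row prints specificity power 0.8879, whereas the exact value for its 63 negatives is 0.8679; the actual alpha printed in that row, 0.0421, is right for 63. A one-digit difference in a table read from PDF by a program may be an extraction error, and no conclusion in the plan relies on that row. It is not part of this point.

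**Conclusion.** The inconsistency is real and small. Section 7.2.1 gives two counts for one quantity, neither equal to 66.7% of 201, and quotes the N=200 power as if it belonged to N=201. Specificity power at N=201 lies between 84.5% and 85.4% depending on the count, so the aim of more than 85% is met with 135/66 and narrowly missed with 134/67 or 133/68. Sensitivity power is about 99.4% in all three cases.

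A reader might infer that the trial is underpowered or needs more patients. The documents do not support that: the whole range spans less than one percentage point.

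The result rests on the plan's own null, alternative and prevalence, and on a one-sided alpha of 0.05. The text does not state that sidedness, but the table's printed alphas and powers reproduce under it.

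**What to change.** In Section 7.2.1:

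- State a single split that follows from the 66.7% prevalence: 134 reference-positive and 67 reference-negative patients of 201.
- Quote the power for that split at N=201: 99.4% for sensitivity and 84.9% for specificity.
- Describe the specificity power as about 85% instead of over 85%.

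If the sponsor did intend 135 positives, the label should read 67.2%, the 133 should go, and the powers should be those for 135/66 (99.4% and 85.4%). The assumed prevalence in the text would then have to match.

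Separately, compare the N=190 specificity power with the source software output, and change it only if the output itself shows 0.8879.

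The cost is the editing of a few numbers in two sentences and one word in the stated aim. No change to enrolment or analysis is needed.
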